6. CONCOMITANT AND DISALLOWED MEDICATIONS

Administration of antibiotic medication within two months prior to the study is an exclusion criterion. Antibiotic administration during the elimination period of the 75 day of protocol will not be disallowed, however, but must be reported to the P.I. No additional treatments or alteration of concomitant medication schedules will be necessary.

7. SUBJECT WITHDRAWALS

Subjects will be advised orally and in writing in the consent forms that they have the right to withdraw from the study at any time without prejudice. Subjects will be withdrawn from the research without their consent in instances of non-compliance or termination of funding for the study. Subjects withdrawn from the study will be replaced with a follow up recruitment.

8. SAFETY AND REPORTABLE EVENTS

At the first visit, subjects will be alerted to self-monitor for any adverse event and to contact study staff by phone or email with any concerns. To monitor subject adverse events, study staff will also contact subjects with a phone call or email within the week subsequent to the last fish meal in each Trial (e.g. between days 15-21 of the Trial). An additional call will be made on day "0" of Trial 2 to monitor effects of prebiotic self-administration. Study staff will not call subjects to monitor adverse events during the intermediate 4-month washout period. The most likely causes for an adverse event would be a reaction to consumption of tuna or the prebiotic administered in the second trial. Subjects will be advised to contact the P.I. by phone or email in the instance that an adverse symptom, sign, illness or experience is encountered. In the instance that this occurs before all tuna meals or prebiotic are consumed, the subject will be advised

to refrain from further fish or prebiotic consumption. Adverse events or problems are not expected but will be reported to the RSRB according to OHSP Policy 801 guidelines.

9. RISK/BENEFIT ASSESSMENT

9A. Potential Risks

The risk of MeHg toxicity from fish consumption remains a topic of considerable debate. MeHg poses the greatest risk for neural development in the fetus and young children, hence, the exclusion of pregnant and breast-feeding women and of children (17yrs and younger) in this study. The risk to adults (18yrs and older) is substantially less. Fish consumption implemented in this protocol will be carefully calculated so that blood MeHg levels incurred will not exceed that of the EPA reference dose (RfD) levels. The EPA reference dose includes a safety factor of 10. Thus, steps to avoid any potential risk due to MeHg have been averted in this study design.

There is a minimal risk of physical discomfort associated with hair collection and with examination for presence of dental amalgam surfaces. There is minimal risk for gastrointestinal discomfort with consumption of prebiotic.

There is a potential risk of infringement on privacy or confidentiality.

Risks of e-mail use:

Sending the subject's information by e-mail has a number of risks that the subject should consider. These include, but are not limited to, the following:

- a) E-mail can be circulated, forwarded, stored electronically and on paper, and broadcast to unintended recipients.
- b) E-mail senders can easily misaddress an e-mail.
- c) Backup copies of e-mail may exist even after the sender or the recipient has deleted his or her copy.
- d) Employers and on-line services have a right to inspect e-mail transmitted through their systems.
- e) E-mail can be intercepted, altered, forwarded, or used without authorization or detection.
- f) E-mail can be used to introduce viruses into computer systems.

9B. Protection Against Risks

Protection against MeHg toxicity will be implemented by careful calculations that consider: 1) the amounts of MeHg administration that will occur in the three fish meals, 2) known kinetic parameters of MeHg accumulation and elimination rates in the blood compartment and 3) each subject's individual body weight and 4) the EPA reference dose (RfD). These calculations are summarized below:

The EPA RfD is derived from a benchmark dose (BMD) analysis using a value of 5.8 μ g/L in blood, which includes a safety factor of 10 (<http://www.epa.gov/iris/subst/0073.htm>).

A study by Kershaw, et al. [4] concludes that 5.9% of a MeHg dose is deposited in the blood compartment after complete tissue distribution.

The blood compartment is ~7.1% of the body mass, equating to a range of 4.2 to 6.5 liters in 130 to 200 pound individuals, respectively.

Therefore, a blood level of 5.8 μ g/L equates to a single dose of:

5.8 μ g/L X (4.2-6.5L) X 1/0.059 = 413-639 μ g MeHg for individuals ranging from 130-200 pounds, respectively.

Fresh tuna steaks have an average mercury content of 0.39ppm* (μ g/g wet weight) One 8oz (227gm) portion of tuna contains 88.5 μ g MeHg. Therefore, three 8oz portions of tuna will give a cumulative dose of 265.5 μ g MeHg, well below that needed to achieve blood levels equal to the EPA RfD.

*A recent in-house analysis of yellowfin tuna tissue obtained from the designated vendor (Wegman's) revealed a mercury content of 0.23-1.35ppm. For this highest level of mercury, three 8oz meals in 14 days would yield MeHg in blood exceeding to the RfD level for a 130-pound person. For this reason, the tuna used in this study will be sampled and analyzed for Hg content prior to distribution to the subjects. Subjects will be allocated tuna steak portion sizes according to their body weight and above calculations to ensure that EPA RfD levels are not exceeded.

Risks of physical discomfort of hair sampling will be managed by limiting sampling to 4-8 strands with each extraction. Subjects will be informed of what to expect with prebiotic administration, which could include feelings of bloating and excess flatulence, which have no adverse health effects beyond being an annoyance.

Privacy will be maintained as best possible by coding samples and storing documents under locked files in the P.I.'s office.

Risk of email breach will be minimized by utilizing teh U of R SecureMail Encryption process following the steps outlined here:

<https://tech.rochester.edu/tutorials/sending-securemail-messages/>

9C. Potential Benefits to Subjects

There will be no direct benefit to individual subjects in this study.

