MeHg impact on human health. Exposure to MeHg through consumption of fish continues to pose a health risk for many populations globally. The developing nervous system is a preferred target for MeHg toxicity, making the fetus and young children most vulnerable. Conflicting results from large epidemiological studies has lead to uncertainty in advising the public on mercury risks associated with fish consumption [1-3]. At odds are the potential harmful effects of Me Hg and the beneficial effects of dietary nutrients and antioxidants in fish. A great deal of uncertainty for this conflict stems from the fact that MeHg metabolism and elimination rate is known to vary widely from individual to individual. This translates into the possibility that two individuals consuming the same amount of fish with the same frequency could, unknowingly, experience as much as 4-fold difference in MeHg in their bodies. Thus, there is a need for greater understanding of the mechanisms of MeHg metabolism and elimination, as well as for development of tools to assess these characteristics in people.

MeHg toxicokinetics: the importance of elimination rate. Orally ingested MeHg is absorbed very efficiently in the intestine with 95% of the dose typically being taken up and distributed to the bloodstream [4]. MeHg undergoes rapid transport and equilibration between blood and target organs [4]. Subsequent to an initial "spike" in concentration, mercury levels in blood resolve to a slow steady rate of decline that is dictated by the overall elimination rate of Me Hg from the body [4-6]. Elimination rates,

expressed as half time ($t_{1/2}$), range from <30 to >120 days, demonstrating the existence of “fast” and “slow” MeHg metabolizers [4-11]. The elimination rate of MeHg is a major determinant for accumulation of MeHg to the elevated steady state levels that occur in people who consume fish on a regular (e.g. weekly or daily) basis. The ability to determine the MeHg metabolism and elimination status of an individual is therefore a means of prospectively identifying “fast” versus “slow” metabolizers.

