participants in the consent form) within the course of approximately 10 months and separated by an intermediate “washout” period of 4 months (Figure 1). Subject will not be required to refrain from fish or seafood during this washout period. Prior to the second trial subjects will receive a commercially available over the counter prebiotic (Prebiotin™) to be orally self-administered on a regular schedule for the entire trial 2 period. This prebiotic is not the subject of this investigation in this study, and is simply selected for its known effects of shifting gut microbial composition to enrich for healthier strains of bacteria (e.g. Bifidobacteria). Fecal sampling prior to and subsequent to prebiotic will be used to document changes in the microbiota for each individual. The prediction is that prebiotic induced change in the gut microbiota will result in a change in MeHg metabolism kinetics in each

individual.

2B. Rationale for Study Design

The main rationale for this study design is based on our evidence that de-methylation of MeHg in the human gut is the driving force for faster elimination MeHg that comes with eating fish. We therefore predict that with the methods we now have available to measure MeHg kinetics, coupled that with high-resolution analyses of gut microbiome characteristics in individual people who have undergone a controlled exposure to MeHg, we can resolve a microbial basis for MeHg metabolism in humans. This is an ambitious undertaking, and hence, is designed as a consortium project to be executed by three investigators with respective expertise in 1) human MeHg kinetics, 2) mouse microbiome manipulations and 3) microbial metagenomics and culturing methods. By design, the human subject component of the study is to be carried out at URMC. The objective is to capture “slow” and “fast” MeHg metabolizing human microbiome samples, that can be handed off to colleagues at MSU for specialized analyses that do not involve the human subjects, simply their de-identified samples.

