Information collected from the subjects at the initial study visit will be: age, sex, body weight, presence/absence of dental amalgams and medications currently taken. This will be collected without the need to access medical records. Subjects will be provided with a notebook carrying templates to fill in for a food diary. Alternatively, subjects who currently use a personal food tracking application (e.g. "My Fitness Pal" or "Healthwatch 360") can substitute a print out from this application of their food consumption record for period spanning the trial.

Fish meal administration. Just prior to each trial, individually weighed, wrapped and frozen portions of tuna steaks in 6-8 oz (170-227gm) portions will be prepared by and purchased from a local market (Wegman's). Portions will be kept frozen in a dedicated freezer in the P.I.'s lab until the time of distribution to the subjects. Frozen fish portions will keep over the time of distribution to enrolling participants (~ 2-3 months, <https://stilltasty.com/fooditems/index/18559>). Tuna portions will be prepared from one large fish fillet, so subjects will be receiving portions from the same fish within each Trial. A sample of the fish tissue will be set aside at the time of purchase to determine mercury content in the fish. Mercury measurements will be performed at the URMC EHSC Elemental Analysis Facility. Fish mercury values will be used to calculate predicted exposures to subjects based on individual body weights (see 9B, Protection

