against risks, below). Where needed, instruction for adjustment of the portion size will be made to assure that MeHg exposure levels will not exceed federal guidelines for each subject. Each subject will be provided with the three frozen portions of tuna in a Thermosafe styrofoam shipping container affixed with prepaid return postage for later return (see below). Two polar-pack freezer blocks will be included to maintain the frozen steaks during transport home. For safety, subjects will be instructed on the steps necessary to keep the fish frozen until preparation for eating. Since cooking does not affect MeHg content in fish, fish meals can be prepared to the subject's own liking and eaten at home. Suggestions for preparation of the fish will be provided to the subjects. Fish meals will be eaten on Days 0, 7 and 14. Subjects will record the date and time of consumption of each meal. Subjects will be instructed not to eat any fish or seafood during the 60 days following the final tuna fish meal. Subjects will be asked to keep a record of all types of food and drink consumed at each meal during the 60-day elimination period using a provided template or their personal food tracking application

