Prebiotic administration. Prebiotin™ (oligosaccharide enriched inulin), a commercially available prebiotic supplement from Jackson GI Medical (<https://www.prebiotin.com/about-us/>), will be distributed to the subjects for self-administration subsequent to the first trial and washout period and prior to the second trial (Figure 1). An intended use for Prebiotin™ is not the subject of investigation in this study. Prebiotic supplementation with this lawfully marketed over-the-counter dietary supplement is being used for its known properties of changing gut microbiome composition. Regarding FDA approval, use of Prebiotin™ in this study will be IND exempt in that all six (6) of the conditions under section 7.1 of Policy 605 of the Office of Human Subject Protection at the Univ. of Rochester are met. Briefly, with respect to Prebiotin™, this study: is not intended to support a new indication for use (7.1.1); is not intended to support a significant change in the advertising of Prebiotin™ (7.1.2); does not involve a change in route of administration, dosage level, or population at risk (7.1.3); will be conducted in compliance with the IRB review (7.1.4); will be conducted in compliance with requirements concerning the promotion and sale of Prebiotin™ (7.1.5); and, does not intend to request exception from informed consent requirements for emergency use (7.1.6). Individually packaged portions (4 grams) of the Prebiotin™ Prebiotic Fiber Stick Pac will be provided to subjects (<https://prebiotin.net/collections/our-products/products/prebiotin-prebiotic-fiber-stick-pac-4g>). Prebiotin™ is the prebiotic of choice in several published studies on gut microbiota control of obesity [20-22] and has been used in an NIH study on reducing inflammation in kidney patients [23]. For this study, we are targeting a dose of 8 grams/day. This dose amount is based on published effects of inulin on gut microbiota in the range of 4 to 16grams/day dosages [20, 24]. We have selected 8 grams/day based on the finding of Holscher et al [24], who demonstrated clear effects on shifting the microbiota composition and activity at the 7.5 gram/day dose level in healthy adults in a controlled double-blinded study. Prebiotin™ self-administration will be initiated one week prior to fish consumption in the second trial and extend through the entirety of the second trial (i.e. 11 weeks, Figure 1). Subjects will be given a 11-week supply of Prebiotin™ Stick Pacs and instructed on how to self-administer on either a once or twice daily dosing schedule. For the first week, subjects will be instructed to begin with a daily supplement of one Pac (4grams) a day, taken with meals. Starting the second week, and additional

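### The section 9B mercury limit has no term for Trial 1 carryover, so study fish alone can push slow eliminators dosed near the limit above 5.8 µg/L in Trial 2

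*Combined protocol and SAP*

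**What the plan says.** Section 9A gives the assurance: "Fish consumption implemented in this protocol will be carefully calculated so that blood MeHg levels incurred will not exceed" the level tied to the EPA reference dose. Section 9B lists the inputs to the calculation, among them "known kinetic parameters of MeHg accumulation and elimination rates in the blood compartment". The calculation it then shows is 5.8 µg/L times blood volume (4.2–6.5 L) divided by 0.059, giving a single dose of 413–639 µg for 130–200 lb. It compares this with 265.5 µg, the content of three 8 oz portions at 0.39 ppm, which is one trial's fish. It also reports that the vendor's tuna has measured 0.23–1.35 ppm, and for that reason sets the rule: "Subjects will be allocated tuna steak portion sizes according to their body weight and above calculations to ensure that EPA RfD levels are not exceeded".

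Section 5C (Fish meal administration) repeats the commitment: "Where needed, instruction for adjustment of the portion size will be made to assure that MeHg exposure levels will not exceed federal guidelines". It also says: "Tuna portions will be prepared from one large fish fillet, so subjects will be receiving portions from the same fish within each Trial".

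On timing, section 2A has the two trials run "within the course of approximately 10 months and separated by an intermediate" washout of four months. Section 5C adds that prebiotic "self-administration will be initiated one week prior to fish consumption in the second trial". Section 1C says half-lives "range from <30 to >120 days".

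**The concern.** The limit is a single-dose figure, but every subject who completes the study is dosed twice. Four months of washout is about one half-life for someone who eliminates with a 120-day half-life, so part of the Trial 1 mercury is still in blood when Trial 2 is eaten. The section names accumulation and elimination as considerations, yet neither enters the sum that portions must follow. No blood or hair mercury result is used to adjust Trial 2 portions.

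What is at stake is the flat statement that the level will not be exceeded, on which subjects and the review board rely. Slow eliminators are not incidental here: Aim 1 sets out to capture slow as well as fast kinetics.

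**Working it through.** **Plan's own figure.** 5.8 × 4.2 / 0.059 = 413 µg and 5.8 × 6.5 / 0.059 = 639 µg. Both reproduce; call this limit L.

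**Inputs**
- Meals on Days 0, 7 and 14 of each trial (5C); each taken as one third of the trial's dose.
- Half-life T from under 30 to over 120 days (1C).
- Gap g from Trial 1 Day 0 to Trial 2 Day 0. A trial ends about Day 74 (5C). With four months as 122 days, g = 74 + 122 = 196. If the prebiotic week follows the washout, g = 203. If two 74-day trials fill about 10 months, g = 304 − 74 = 230.
- Study fish only; no other dietary mercury.

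**Model (an assumption).** One compartment, first-order decay with k = ln 2 / T, the same T throughout. With t = 0, 7, 14:
- f2 = mean of exp(−k(14 − t)), the share of the Trial 2 dose left at Trial 2 Day 14.
- f1 = mean of exp(−k(g + 14 − t)), the share of the Trial 1 dose left on that day.
- With both trials at L, the level is 5.8 × (f1 + f2).

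**At T = 120 days.** f2 = 0.961; f1 = 0.310, 0.298, 0.255 for g = 196, 203, 230. Trial 1 alone peaks at 5.8 × 0.961 = 5.57 µg/L, below the ceiling, so any excess is carryover.

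| Half-life (days) | Trial 2 Day 14 level, both trials at L (µg/L), g = 196 / 203 / 230 |
|---|---|
| 30 | 5.03 / 5.02 / 5.00 |
| 50 | 5.63 / 5.60 / 5.50 |
| 80 | 6.47 / 6.41 / 6.21 |
| 120 | 7.37 / 7.30 / 7.05 |

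**Break-even half-life** (f1 + f2 = 1): 55.9, 57.3, 62.6 days.

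**How near the limit dosing must be.** At 120 days, equal doses in both trials breach above 1/(f1 + f2) = 0.787, 0.795, 0.823 of L. Taking the two ends of that range, with three 8 oz portions weighing 681 g and three 6 oz portions 510 g:
- 130 lb: 325–340 µg, which is 0.48–0.50 ppm at 8 oz or 0.64–0.67 ppm at 6 oz.
- 200 lb: 503–526 µg, which is 0.74–0.77 ppm at 8 oz or 0.99–1.03 ppm at 6 oz.

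All lie inside the vendor's 0.23–1.35 ppm. The full limit is reached with 8 oz portions at 413/681 = 0.61 ppm (130 lb) and 639/681 = 0.94 ppm (200 lb).

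**Mixed case, 130 lb.** An average Trial 1 adds 265.5 × 0.059 / 4.2 = 3.73 µg/L before decay. Followed by Trial 2 at L, the level at 120 days is 5.8 × f2 + 3.73 × f1 = 6.73, 6.68, 6.52 µg/L; break-even is 63.9, 65.5, 71.3 days. One high-mercury fillet, in Trial 2, is enough.

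**Average tuna in both trials, 130 lb.** 3.73 × (f1 + f2) = 4.74, 4.69, 4.53 µg/L at 120 days and about 3.2 at 30 days. No breach.

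**The case against.** **The formula may be only a summary.** Section 9B says its calculations are summarised, portions are prepared just before each trial, and nothing states that Trial 1 residue will be ignored. That the limit starts from zero is indeed an inference. But the rule ties portions to the calculation shown, and naming kinetics as a consideration does not supply a carryover term.

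**The assurance may be per trial.** Item 1 in 9B refers to three meals, and for one trial alone the limit holds. The wording in 9A covers fish consumption under the protocol, which most naturally includes both trials. If a per-trial meaning was intended, it should be stated.

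**The half-life may not be constant.** Section 1D says it varies within a person, and the Trial 2 prebiotic is meant to change it. This weakens the top figures: 120 days in both trials but 60 during the interval between them gives about 6.2–6.5 µg/L. That is still above 5.8.

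**The 5.9% may apply to absorbed dose.** With the 95% uptake in section 1C, the 120-day level becomes 6.7–7.0 µg/L and break-even 67–75 days. The conclusion narrows but stands.

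**A breach needs two conditions together.** It takes a slow eliminator and a high-mercury fillet, and the documents give a distribution for neither. This stands in full: frequency is unknown, and for a 200 lb subject the fish must be about twice the 0.39 ppm average or more.

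**Conclusion.** The concern holds, as a minor point. The arithmetic of the limit is correct, but the guarantee drawn from it does not follow for subjects with half-lives above about 56–63 days who are dosed near the limit. At 120 days the excess is 1.25–1.57 µg/L (7.05–7.37 against 5.8), about 22–27%. Fast eliminators are within the ceiling, as are subjects given average tuna in both trials at half-lives up to 120 days. The result rests on one-compartment first-order decay, equal meals, a constant half-life and a 196–230 day gap, and it counts study fish only. The safety factor of 10 in the 5.8 µg/L figure, and the exclusion of pregnant and lactating women, mean that the defect is in the accuracy of the assurance.

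**What to change.** Set the Trial 2 limit to the smaller of L and (L − D1 × f1) / f2, where D1 is the subject's Trial 1 dose. Use a 120-day half-life for everyone (f2 = 0.96, f1 = 0.31–0.25 depending on the gap), so that dose does not depend on the half-life measured in Trial 1. The results are:
- After a full-limit Trial 1: 297–320 µg at 130 lb and 459–496 µg at 200 lb. This still admits the 265.5 µg average case.
- After an average Trial 1 at 130 lb: 344–359 µg.

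State in 9A and 9B that the assurance covers mercury from study fish across both trials, assumes a half-life of up to 120 days, and does not cover other fish, which subjects may eat during the washout.

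The data are already held (Trial 1 dose, body weight, meal dates) and portions are already set trial by trial, so the change is one added term and some wording.

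There are three costs. After a full-limit Trial 1 the Trial 2 limit falls by 22–28%, so with high-mercury fish the hair peaks that calibrate growth rate may be smaller. The lower Trial 2 dose would coincide with the prebiotic in the paired comparison; a half-life taken from a first-order log slope does not depend on dose, but precision could suffer. One equal limit for both trials, at 79–82% of L, would avoid the imbalance at the price of a lower Trial 1 limit. Finally, subjects slower than 120 days stay uncovered: at an illustrative 150 days, the level under the proposed limit after a full-limit Trial 1 is about 6.3 µg/L.
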